2.4 Secondary Criteria for Evaluation

1. Proportion of clinical improvement at Day 14, defined as a \geq 2-point improvement from Day 1 on a 7-point ordinal scale
2. Timing and duration (days) of Remdesivir
3. Severity of disease on Day 7, Day 14 and Day 28 based on NEWS 2 score
4. Clinical status assessed by a 7-point ordinal scale on Day 28 (or at last observation if discharged or died prior to this time point) in those still hospitalised after day 14.
5. Time to SpO₂ $>$ 94% on room air (number of days when evaluation made on day 7, 14 or 28)
6. Duration of oxygen therapy (total days)
7. Admitted to ICU
8. Need for and time on mechanical ventilation/ECMO of hospitalisation
9. Duration of hospitalisation

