4.2 Study Variables

All the study variables are summarized in the following table.

	Day1 (Hospital Admission) baseline	Day 7 (+/- 1 day) and Day14 (+/- 2 days) / last observation if discharged or died prior to these time points.	Day 28 or last observation after Day 14 if discharged or died prior to this time point.
Medical History ^a	x		
Pregnancy test	x		
HIV test	x		
Vital Signs ^b	x	x	x
Laboratory Testing ^c	x	x	x
Oxygenation ^d	x	x	x
Clinical Status ^e	x	x	x
Other Treatments for COVID-19 ^f	x	x	x
NEWS SCORE ^g	x	x	x

a. Focused medical history and also the following information (e.g. demographics including ethnicity, baseline characteristics including DM, CV disease and COPD)

b. SpO2, body temperature, body weight and height on admission

c. Includes white blood cell count, creatinine, total bilirubin, ALT, AST at admission Day 7 and day 14 or at discharge if before day 14, radiographic findings at baseline and as available and SARS-CoV-2 PCR, antigen and/or antibody testing.

d. Includes oxygen supplementation: room air, low flow O2 (L/min and %), high flow O2 (L/min and %), non-invasive positive pressure ventilation (FiO2 or %), mechanical ventilation (FiO2 or %), ECMO (extracorporeal membrane oxygenation)

e. The ordinal scale is as: 1. Death, 2. Hospitalised, on invasive mechanical ventilation or ECMO, 3. Hospitalised, on non-invasive ventilation or high flow oxygen devices, 4. Hospitalised, requiring low flow supplemental oxygen, 5. Hospitalised, not requiring supplemental oxygen - requiring ongoing medical care (COVID-19 related or otherwise), 6. Hospitalised, not requiring supplemental oxygen - no longer requires ongoing medical care, 7. Not hospitalised

f. These include corticosteroids, anticoagulants, azithromycin/other antibiotics, anti-inflammatory agents (e.g. Tocilizumab), investigational agents (eg hydroxychloroquine) and immunotherapies such as convalescent plasma and monoclonal antibodies.

g. NEWS 2 score is based on Respiration rate (per minute), SpO2 (%) Air or oxygen. Systolic blood pressure (mmHg), Pulse (per minute) Consciousness, Temperature (°C)

For the purpose of the analyses, partial dates will be extrapolated. For example, all dates saved as NK/FEB/2020 will be recoded as 15/FEB/2020 and those saved NK/NK/2020 will be recoded as 15/JUNE/2020. NK means not known.

5. Sample Size calculation

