8.1 Primary Efficacy Analysis

Primary endpoint	
 Occurrence of death within 28 days
Analysis population	
 Full population analysis
Descriptive statistics and graphical representation	
 Data will be summarized with proportion and 95% confidence interval globally and according to disease severity at baseline (ORDSC score 2 vs 3-4 vs 5) LogRank test will be used to compared the 3 groups P-values will be two-tailed with a significant level at 5%. Kaplan-Meier curves will be plotted
Statistical analysis	
Kaplan-Meier estimates will be used to calculate the proportions and the 95% confidence intervals
 
Time to death will be defined as the time between the date of hospitalization and the date of death or discharge from hospital or last observation
 
Participant with missing clinical status or alive at day 28 will be censored at the date of last observation

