Descriptive statistics and graphical representation	
 Data will be summarized with mean and 95% confidence interval globally and according to disease severity at baseline (ORDSC score 2 vs 3-4 vs 5) Linear mixed models will be used to compared the 3 groups P-values will be two-tailed with a significant level at 5%. The evolution curves will be plotted
Statistical analysis	
The changes from baseline in NEWS 2 score within group will be compared using mixed models for repeated measures with random intercept and unstructured covariance matrix, adjusted for baseline value. Subjects who die will be imputed as a score of 20 and subjects who are discharged will be imputed a score of 2. The sample size is quite large to consider the residuals of the mixed model is normally distributed. Time will be considered as categorical variable

Endpoints	3.1. Occurrence of SpO2 >94% on room air on day 7, 14 and 28 3.2. Time to SpO2 > 94% on room air
Analysis population	
 Full population analysis
Descriptive statistics and graphical representation	
 Data will be summarized with proportion and 95% confidence interval for the occurrence of SpO2 >94% on room air and median and 95% confidence interval for time to SpO2>94%. Data will be summarized globally and according to disease severity at baseline (ORDSC score 2 vs 3-4 vs 5)

	
 • LogRank test will be used to compared the 3 groups • P-values will be two-tailed with a significant level at 5% • Kaplan-Meier curves will be plotted
Statistical analysis	
Kaplan-Meier estimates will be used to calculate the proportion and the median time as well as the associated 95% confidence intervals
 
Time to event will be defined as the time between the date of first symptom and the date of the event of interest or hospital discharge or last observation
 
Subjects who died with $\text{SpO}_2 \leq 94\%$ will be censored at day 28

Endpoints	4.1. Frequency of oxygen therapy overall and by type (low versus high flow oxygen) 4.2. Duration (days) of oxygen therapy 5. Frequency of ICU admission 6. Number of days spent in ICU/ITU 7.1. Frequency of mechanical ventilation/ECMO of hospitalization 7.2. Time on mechanical ventilation/ECMO
Analysis population	
 • Full population analysis

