Descriptive statistics and graphical representation	
 • Data will be summarized with proportion or median and 95% confidence interval according to the endpoint • Data will be summarized globally and according to disease severity at baseline (ORDSC score 2 vs 3-4 vs 5) • LogRank test will be used to compared the 3 groups • P-values will be two-tailed with a significant level at 5% • Kaplan-Meier curves will be plotted
Statistical analysis	
Kaplan-Meier estimate will be used to estimate the proportion of subject with oxygen therapy and by type (low versus high flow oxygen), the proportion of subjects admitted in ICU and the proportion of those having received mechanical ventilation or ECMO. Time to event will be defined as the time between the date of first symptom and the date of event of interest. Participants not experienced the event of interest will be censored at last observation date. Participants who deceased before will be considered as having the event.
 
The duration (days) of oxygen therapy, the number of days spent in ICU/ITU and the time (days) on mechanical ventilation/ECMO will be estimated using Kaplan-Meier estimates as well as the associated 95% confidence intervals. The time will be defined as the time between the start date of event and the end date of the event of interest or hospital discharge. Subjects who died will be censored at day 28.

Endpoint	8. Duration (days) of hospitalization
----------	----------------------------------------------

Analysis population	
 Full population analysis
Descriptive statistics and graphical representation	
 Data will be summarized with median and 95% confidence interval globally and according to disease severity at baseline (ORDSC score 2 vs 3-4 vs 5) LogRank test will be used to compared the 3 groups P-values will be two-tailed with a significant level at 5% Kaplan-Meier curves will be plotted
Statistical analysis	
Kaplan-Meier method will be used to calculate the medians and the 95% confidence intervals. Time (days) from hospitalization to hospital discharge will be defined as the time between the date of hospitalization for COVID-19 and the date of hospital discharge. The event will be hospital discharge. Subjects who died will be censored at day 28.

9. Other Analyses

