	Alert				
	Verbal				
	Pain				
	Unresponsive				

NEWS 2 score, median (IQR)						
	Low (score 0-4), n(%)					
	Medium (score 5-6)					
	High (score 7 or more)					
COVID Vaccination, n(%)						
Other treatment for COVID-19, n (%)						
	Corticosteroids					
	Tocilizimab/Sarilumab					
	Other COVID Treatment Related Drug					

Table 2. Primary and secondary outcomes

	Overall Total N=xxx	Ordinal Scale Category			
		Score of 2 N=xxx	Score of 3-4 N=xxx	Score of 5 N=xxx	P- value
Mortality over entire study period					
Number of deaths by Day 28					
Kaplan-Meier estimate of mortality by Day 28 – % (95% CI)					
Ordinal Scale at day 7 (± 1 day) – no. (%)					
1					
2					
3					
4					
5					
6					
7					
Ordinal Scale at day 14 (± 2 days) – no. (%)					
1					
2					
3					
4					
5					
6					
7					
Ordinal Scale at day 28 (± 2 days) – no. (%)					
1					
2					
3					
4					
5					
6					
7					
Disease severity assessed by NEWS 2 Score at 7 days					
Total N					
Mean NEWS 2 Score at days 7 (95% CI)					
Disease severity assessed by NEWS 2 Score at 14 days					
Total N					
Mean NEWS 2 Score at days 14 (95% CI)					
Disease severity assessed by NEWS 2 Score at 28 days					

Total N					
Mean NEWS 2 Score at days 28 (95% CI)					
SpO2>94% over first 7 days					
Number of SpO2>94% by Day 7					
Kaplan-Meier estimate of by Day 15 – % (95% CI)					
SpO2>94% over first 14 days					
Number of SpO2>94% by Day 14					
Kaplan-Meier estimate of SpO2>94 by Day 14 – % (95% CI)					
SpO2>94% over entire study period					
Number of SpO2>94% by Day 28					
Kaplan-Meier estimate of SpO2>94 by Day 28 – % (95% CI)					
Median time to SpO2>94% (95% CI) - days					
Oxygen therapy over entire study period (low or high flow)					
Number of oxygen therapy by Day 28					
Kaplan-Meier estimate of oxygen therapy by Day 28 – % (95% CI)					
Median duration on oxygen therapy (95% CI) - days					
Low flow oxygen therapy over entire study period					
Number of low flow oxygen therapy by Day 28					
Kaplan-Meier estimate of low flow oxygen therapy by Day 28 – % (95% CI)					
High flow oxygen therapy over entire study period					
Number of high flow oxygen therapy by Day 28					
Kaplan-Meier estimate of high flow oxygen therapy by Day 28 – % (95% CI)					
ICU admission over entire study period					
Number of ICU admission by Day 28					
Kaplan-Meier estimate of ICU admission by Day 28 – % (95% CI)					
Median duration spent in ICU (95% CI) - days					

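### SAP 8.2 counts time to SpO2 >94% from first symptom, but reports it by Day 7, 14 and 28, which the study schedule counts from hospital admission

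*SAP*

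**What the plan says.** - **Clock for SpO2 (SAP 8.2, endpoints 3.1-3.2):** "Time to event will be defined as the time between the date of first symptom and the date of the event of interest", or to hospital discharge or last observation. Kaplan-Meier gives both the proportions and the median. Patients who die with SpO2 at or below 94% are censored at day 28, with no origin named for that day.
- **Clock for oxygen therapy, ICU admission and ventilation/ECMO frequencies (SAP 8.2, endpoints 4.1, 5 and 7.1):** "Time to event will be defined as the time between the date of first symptom and the date of event of interest".
- **Study days:** the SAP 4.2 schedule heads its first column "Day1 (Hospital Admission) baseline". Protocol section 5 also makes hospital admission Day 1.
- **Protocol criterion (2.4, item 5):** time to SpO2 >94% is the "number of days when evaluation made on day 7, 14 or 28".
- **Primary endpoint (SAP 8.1), for comparison:** "Time to death will be defined as the time between the date of hospitalization and the date of death". Duration of hospitalisation (endpoint 8) also starts at hospitalisation.
- **Table 2 (SAP Appendix):** SpO2 >94% is reported by Day 7, 14 and 28. In the Day 7 block the count row reads "Number of SpO2>94% by Day 7", but the Kaplan-Meier row below it reads "Kaplan-Meier estimate of by Day 15". Oxygen therapy, ICU admission and ventilation/ECMO are reported by Day 28.

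**The concern.** Table 2 gives a Day 28 Kaplan-Meier figure for mortality and another for SpO2 under the same day label, one counted from hospitalisation and the other from first symptom. A reader will take both as hospital-day results. The SpO2 figures would cover a shorter hospital period and so come out too low.

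The median time to SpO2 >94% would include illness before admission. Without delayed entry, patients count as at risk over days when no in-hospital event could be recorded. If the lag from symptoms to admission differs between the baseline severity groups, the planned log-rank comparison would also mix lag with recovery.

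**Working it through.** The plan gives no figure to reproduce. The check compares the two clocks and then illustrates the size.

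**Inputs.** From the documents: origin at first symptom (SAP 8.2), Day 1 at admission (SAP 4.2, Protocol 5), rows at Days 7, 14 and 28 (Table 2). Not in the documents, so assumed: lag L from first symptom to admission of 3, 7 or 10 days; exponential recovery with a median of 7 days from admission to SpO2 >94%.

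**Step 1: shift.** A point c days after first symptom is c − L days after admission. For rows 7/14/28 this gives 4/11/25 days at L = 3, 0/7/21 at L = 7, and −3/4/18 at L = 10.

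**Step 2: SpO2 dated daily, one lag for all.** The proportion recovered x days after admission is F(x) = 1 − 2^(−x/7), and zero for x ≤ 0. The admission clock reads F(c); the SAP clock reads F(c − L).

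| Clock | Day 7 | Day 14 | Day 28 | Day 28 loss (points) |
|---|---|---|---|---|
| Admission | 50.0% | 75.0% | 93.8% | – |
| First symptom, L = 3 | 32.7% | 66.4% | 91.6% | 2.2 |
| First symptom, L = 7 | 0% | 50.0% | 87.5% | 6.2 |
| First symptom, L = 10 | 0% | 32.7% | 83.2% | 10.6 |

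The median rises from 7 to 7 + L days.

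**Step 3: lag varying between patients.** A simulation of 400,000 patients with the same recovery curve and a gamma lag (shape 4) gives, by Day 7/14/28:
- mean lag 3: 32.1/66.0/91.6%, median 10.1 days;
- mean lag 7: 11.6/47.9/86.7%, median 14.4 days;
- mean lag 10: 5.4/33.5/80.7%, median 17.7 days.

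The zeros in step 2 come from giving everyone the same lag. The direction and the general size remain.

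**Step 4: SpO2 dated only at nominal visits, everyone still in hospital.** Hospital Day k is k − 1 days after admission, so L + k − 1 days after first symptom. For L = 2 to 8 the Day 7, 14 and 28 visits fall at 8-14, 15-21 and 29-35 days. The Day 14 row then holds only what was seen at the Day 7 visit, and the Day 28 row only what was seen by the Day 14 visit. On the admission clock, F(6)/F(13)/F(27) = 44.8/72.4/93.1%. On the SAP clock the rows read 0/44.8/72.4%. The Day 28 loss is 93.1 − 72.4 = 20.7 points.

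**Step 5: other recovery times.** With a median of 5 days the Day 28 loss is 1.1, 3.4 or 6.2 points (daily-dated, L = 3, 7, 10) and 14.1 points (visit-dated). With a median of 10 days it is 3.3, 9.0 or 14.4 points and 25.2 points.

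**Step 6: is moving the origin enough?** The Day 14 window is ±2 days, so a valid assessment can fall on hospital Day 16, which is 15 days after admission. A row read at 14 days would still miss it. A rule assigning in-window visits to rows is needed as well.

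**The case against.** The strongest defence is that the first-symptom origin is deliberate. It is written out twice in SAP 8.2, symptom onset is a natural clock for an infection, Table 2 does not define its days, and Protocol 2.4 names no time origin. Part of this stands: a symptom clock is not invalid in itself, and relabelled rows with delayed entry would also be coherent. But the rows are not relabelled and delayed entry is not provided. Only the schedule defines the days, and it starts at admission; Table 2 uses the schedule's Day 7 and Day 14 windows for the ordinal scale. Where the SAP wants both origins it names them, as in endpoints 9.1 and 9.2. The protocol's objective that mentions first symptoms concerns the timing of remdesivir only.

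A second objection is that the visit-dated loss is overstated. This stands. The schedule uses the "last observation if discharged or died prior to these time points", so patients discharged early can enter a row before the next visit. Step 4 excludes them, although most have recovered by then. A reader might infer that about 21 points is the expected error; the documents do not support that.

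Third, the exact lag at which a nominal visit leaves its own row depends on the day count: 2 days if elapsed days are used, 1 day if the day of first symptom is called Day 1. The documents do not settle this, so the point does not rest on that threshold.

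Fourth, the Day 15 label is a misprint. It is not evidence about the origin.

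**Conclusion.** The mismatch is established from the text: the clock starts at first symptom, while the day labels belong to a schedule that starts at admission. Each SpO2 row covers about L fewer hospital days than its label says, and the median includes L unobserved days.

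The true size is unknown, because neither the lag nor the recovery time is in the documents. Under the assumed 7-day median with daily dating, the Day 28 percentage loses about 2 to 11 points for lags of 3 to 10 days. The Day 7 row falls from 50% to 33% at L = 3, and to 0% at a common lag of 7 days or more. About 21 points at Day 28 is an upper-end case for that median.

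For oxygen therapy, ICU admission and ventilation/ECMO, the effect on the Day 28 rows is probably small. A reader might infer that baseline score already settles oxygen use in scores 2 and 3-4. It does not: score 2 is invasive ventilation or ECMO and score 3 includes non-invasive ventilation, neither of which is by definition low or high flow oxygen.

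Nor does the point reach the primary endpoint, which is timed from hospitalisation. Durations 4.2, 6 and 7.2 run from the start of each event and are also unaffected. The affected endpoints are secondary, in a study with no formal hypothesis. The SAP should be fixed, but the main result is not in question.

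**What to change.** 1. In the two SAP 8.2 cells, define time to event for endpoints 3.1-3.2, 4.1, 5 and 7.1 from the date of hospitalisation, as for the primary endpoint and endpoint 8.
2. State one day count, with admission as Day 1, and use it for both event times and row cut-offs.
3. Count each in-window scheduled SpO2 assessment at its nominal day (Day 7 ±1, Day 14 ±2, and Day 28 with its window), so that it falls in its own row. State the Day 28 window: the schedule prints none, and Table 2 prints ±2 days only for the ordinal scale. Use the actual date for a last observation before discharge or death.
4. State that day 28 in the SpO2 censoring rule is counted from admission, and put the count rows in Table 2 on the same clock.
5. As a separate label correction, make the Kaplan-Meier row in the Day 7 block name SpO2 >94% and Day 7.
6. If a symptom-onset clock is also wanted, report it as supplementary, with delayed entry at admission and rows labelled as days since first symptom.

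The cost is small: two reworded cells, short statements on day count and visit windows, and one table label. No new data are needed, since the hospitalisation date already drives the primary endpoint. Endpoint 9.1 minus endpoint 9.2 gives each patient's lag if it is to be described. The downside is that the main SpO2 result no longer describes time since illness onset.

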- f. These include corticosteroids, anticoagulants, azithromycin/other antibiotics, anti-inflammatory agents (e.g. Tocilizumab), investigational agents (eg hydroxychloroquine) and immunotherapies such as convalescent plasma and monoclonal antibodies.
- g. NEWS 2 score is based on Respiration rate (per minute), SpO2 (%) Air or oxygen. Systolic blood pressure (mmHg), Pulse (per minute) Consciousness, Temperature (°C)

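### SAP 8.2: the death rule for room-air SpO2 recovery omits the room-air condition; read literally, some deaths are censored at about the time of death and the Day 28 recovery proportion is biased upward

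*SAP*

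**What the plan says.** SAP 8.2 defines endpoints 3.1 and 3.2 by two conditions together: saturation above 94%, and breathing room air. The second endpoint is "3.2. Time to SpO2 > 94% on room air". The method is given as "Kaplan-Meier estimates will be used to calculate the proportion and the median time as well as the associated 95% confidence intervals". The clock starts at first symptom and runs to "the date of the event of interest or hospital discharge or last observation". One sentence deals with death: "Subjects who died with $\text{SpO}_2 \leq 94\%$ will be censored at day 28".

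Four other places bear on it:

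- For the durations of oxygen therapy, ICU stay and ventilation, and for hospital stay, the SAP 8.2 rule is "Subjects who died will be censored at day 28", with no saturation condition.
- SAP 4.2, note d, records oxygen support from room air up to ECMO as an item separate from SpO2. Protocol section 5, footnote g, lists among the NEWS 2 components "SpO2 (%) Air or oxygen".
- SAP section 3 heads endpoint 3 as a room-air measurement and keeps that condition in both sub-endpoints.
- Table 2 of the SAP Appendix drops the condition from its SpO2 rows, for example "Number of SpO2>94% by Day 28".

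**The concern.** The endpoint has two conditions and the death rule negates only one of them. Support exists to raise saturation, so a last reading above 94% on oxygen or a ventilator shortly before death is to be expected in some patients. Such a patient never recovered on room air, yet the rule that keeps deaths in the risk set does not reach them.

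Censoring at death tells the Kaplan-Meier estimator that the patient would have gone on to recover at the rate of those still at risk. Death rules recovery out, so the estimated proportion recovering is too high. Two patients with the same outcome (died, never above 94% on room air) would be treated in opposite ways because of a reading that depends on the support they were receiving.

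**Working it through.** **Step 1: which rule applies to whom.** Take patients who die without ever meeting the endpoint.

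| Last SpO2 | Rule that applies | Handling |
|---|---|---|
| 94% or less, on air or support | the death rule | non-event, held to Day 28 |
| above 94%, on support | none specific; default end of follow-up | no event and no live discharge, so last observation, at about death |

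The second row is an inference from the default. The SAP does not state it, but no other provision covers these patients.

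**Step 2: inputs.** The documents give no mortality rate, no recovery rate and no share of deaths with SpO2 above 94% on support. There is therefore no planned figure to reproduce, and all rates below are assumptions. The one documented input is the planned size of at least 450 cases.

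**Step 3: direction, in closed form.** Assume constant hazards. Let r be the proportion recovered by Day 28, d the proportion dead without recovery, and s the share of those deaths censored at death. Put S = 1 - r - d, p = d/(r + d) and q = (1 - s)p. Then

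KM(28) = 1 - [q + (1 - q)S]^((1 - p)/(1 - q)).

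With s = 0 this equals r, the true proportion, and it rises with s. For r = 0.60 and d = 0.20: S = 0.20 and p = 0.25. At s = 0.5, q = 0.125, the bracket is 0.125 + 0.875 × 0.20 = 0.30, the exponent is 0.75/0.875 = 0.857, and KM = 1 - 0.30^0.857 = 0.644, a rise of about 4.4 points (simulation gave 4.3). At d = 0.10 and d = 0.05, still with s = 0.5, the result is 0.621 and 0.610: rises of 2.1 and 1.0 points.

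**Step 4: a second model with less extreme rates.** Survivors' recovery time is lognormal with median 9 days and sigma 0.75 (distribution R, density f). Deaths are uniform over Days 4-28 (distribution D). The number at risk is proportional to

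Y(t) = (1 - d)(1 - R(t)) + d(1 - s) + d·s·(1 - D(t)),

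and KM(28) = 1 - exp(-∫ (1 - d) f(t)/Y(t) dt), integrated over 0 to 28. With all deaths held (s = 0) this is (1 - d) × R(28), where R(28) = 0.935.

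| Mortality | All held | s = 10% | s = 30% | s = 60% |
|---|---|---|---|---|
| 10% | 0.841 | 0.846 | 0.856 | 0.872 |
| 15% | 0.795 | 0.801 | 0.814 | 0.837 |
| 40% | 0.561 | 0.570 | 0.589 | 0.628 |

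At 10-15% mortality the rise is 1.4 to 4.2 points for shares of 30-60%, and 0.5 to 0.6 point for a share of 10%.

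**Step 5: median.** At s = 60% it moves from 9.99 to 9.92 days (10% mortality) and from 10.64 to 10.50 days (15%). In the 40% scenario it moves from 18.6 to 16.3 days.

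**Step 6: scale.** At N = 450 the 95% half-width is 1.96 × √(0.84 × 0.16/450) = 3.4 points, or 3.7 points at 0.795.

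**Limits.** Neither model includes the symptom-based clock or the ending of follow-up at discharge. Seeing recovery only at Days 7, 14 and 28 raises the bias somewhat: in the Step 3 example with d = 0.20 and s = 0.5, from 4.3 to 5.3 points by simulation.

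**The case against.** The strongest reply is that the rule is shorthand. SAP section 3 introduces this endpoint as SpO2 on room air, and SAP 8.2 itself shortens the endpoint to a bare saturation threshold when it describes the median. On that convention, dying at 94% or less just means dying without reaching the endpoint. The neighbouring rules, which hold all deaths to Day 28, suggest the same intent, and the bias is then zero. This reading is plausible and cannot be excluded. It does not remove the problem, because nothing in the text selects it, and a programmer who applies the sentence as written gets a different answer.

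A second reply is that the effect is small. For a 95% interval at N = 450, most of the 1.5 to 4 point range lies within the half-width, and the share of affected deaths is unknown. That is fair on importance. But the error runs in one direction and does not shrink as more patients are enrolled.

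A third is that the models are not the SAP's analysis. That also stands: the figures show direction and order of size and do not predict the study's result.

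**Conclusion.** The wording gap is real. Under the literal reading the room-air recovery proportion is biased upward whenever any such death occurs. The size is about 1.5 to 4 points at Day 28 with 10-15% mortality and 30-60% of deaths above 94% on support, and about half a point at a 10% share, all on assumed rates. The endpoint is secondary and descriptive, the SAP tests no formal hypothesis, and the Day 28 mortality analysis is untouched.

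A reader might infer more than the documents support:

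- *That the SAP instructs censoring at death.* It does not say so; this follows from a literal death rule combined with the default.
- *That the median is materially too early.* Overall it shifts by about 0.1 day in the 10-15% mortality scenarios.
- *That the log-rank comparison by severity is shown to be distorted.* A larger effect is possible where mortality is high, as the 40% scenario illustrates. But the documents give no stratum rates, no log-rank test was simulated, and high flow is pooled with low flow in the ORDSC 3-4 group.
- *That following Table 2 would count these deaths as recoveries.* In the Step 4 model that would add s × d, or 3 to 9 points (0.30 × 10% to 0.60 × 15%). The written endpoint keeps the room-air condition, so this is not an analysis the SAP describes.

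**What to change.** In SAP 8.2, replace the death rule for endpoints 3.1 and 3.2 with: *Subjects who die without a recorded SpO2 >94% on room air are kept as non-events to Day 28, whatever their last SpO2 on oxygen.* Alongside it:

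- State the origin of Day 28 for this endpoint. Its clock starts at first symptom, while the study days in SAP 4.2 start at admission.
- Derive the event from SpO2 above 94% and oxygenation recorded as room air at the same assessment.
- Add the room-air condition to every SpO2 row of Table 2, for consistency.

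The cost is a few lines of SAP text and table labels. No new data are needed, because oxygenation is scheduled at the same visits as SpO2. The downside is a recovery figure that may be slightly less favourable. If the sponsor always meant the shorthand reading, the results do not change and the text becomes unambiguous.

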2.2 Secondary objectives

The secondary objectives are to assess the clinical course and outcome of adults with COVID-19 who have been treated with Remdesivir with respect to the following:

1. a 7-point ordinal clinical status scale on Day 7 and Day 14
2. timing (from first symptoms and from hospitalisation) and duration of use of Remdesivir
3. clinical severity at Day 7, 14, 28 as assessed by the NEWS 2 score
4. clinical status as assessed a 7-point ordinal scale on Day 28 (or at last observation if discharged or died prior to this time point) in those still hospitalised after Day 14.
5. SpO₂ > 94% on room air on day 7, 14 and 28
6. duration and type (low versus high flow) of oxygen therapy (days)
7. admitted to ICU (yes versus no)
8. number of days spent on ICU/ITU
9. use of mechanical ventilation/ECMO (extracorporeal membrane oxygenation); start and stop dates
10. re-admission with COVID-19 complications or recurrence within 28 days of discharge and outcome (discharged or deceased)

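### SAP 8.2 counts deaths without oxygen, ICU admission or ventilation/ECMO as having had it, so percentages labelled as treatment use are unnamed 'treatment or death' composites

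*SAP*

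**What the plan says.** SAP 8.2 treats endpoints 4.1, 5 and 7.1 in one block. The first is labelled "4.1. Frequency of oxygen therapy overall and by type (low versus high flow oxygen"); the other two are likewise named as frequencies, of ICU admission and of mechanical ventilation/ECMO. The statistical-analysis cell says Kaplan-Meier will estimate the proportion with oxygen therapy, overall and by type, and also "the proportion of subjects admitted in ICU and the proportion of those having received mechanical ventilation or ECMO". Time runs from first symptom.

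Two rules follow for patients without the event. "Participants not experienced the event of interest will be censored at last observation date". Then: "Participants who deceased before will be considered as having the event". For the comparison by baseline severity (score 2, 3–4, 5), "LogRank test will be used to compared the 3 groups", at a two-sided 5% level.

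The durations in the same block (endpoints 4.2, 6 and 7.2) follow a different death rule, censoring at day 28. They are not part of this point.

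Table 2 in the SAP appendix gives each treatment a count by day 28 and a Kaplan-Meier percentage by day 28. Neither mentions death. Protocol 2.2 states the ICU objective as a plain binary: "admitted to ICU (yes versus no").

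**The concern.** Once a death before the treatment counts as the event, the curve estimates the probability of treatment or death, whichever comes first. A patient who dies on the ward without an ICU stay is counted as an ICU admission. No endpoint name, table row, footnote or protocol objective says so, and no version without these deaths is planned.

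The by-type oxygen rows have the same problem in a sharper form. SAP 4.2, footnote d, records the modes of support as separate categories ("low flow O2 (L/min and %), high flow O2 (L/min and" so on, then non-invasive and mechanical ventilation). A patient who dies with no record of one oxygen type is still counted as having had that type.

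At stake is what the published percentages mean. Readers will take them as the share of remdesivir-treated patients who needed oxygen, intensive care or ventilation. The group contrasts would likewise mix mortality, which is already the primary endpoint, with use of care. The SAP also does not say whether the counts in Table 2 include the assigned deaths, so a count and the percentage beside it may not agree.

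**Working it through.** The plan states no expected mortality, treatment frequency or power, so there is no figure of its own to reproduce. The size has to be shown over assumed ranges.

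**Inputs**
- Cohort size: 450 (SAP 4.1, planned minimum).
- Assumed: v, the proportion who received the treatment; m, mortality by the day the curve is read; q, the share of deaths that had received the treatment first.

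**Formula.** With nobody censored before day 28, Kaplan-Meier is the simple proportion with an event, so

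- quantity under the SAP rule = v + m(1 − q)
- quantity that the labels describe = v
- excess = m(1 − q)

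The excess does not depend on v, and it is zero only if every patient who died had first received the treatment. The identity is the same whether time starts at first symptom or at admission; only the deaths that fall within the window change.

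**ICU admission or ventilation/ECMO** (assumed m = 10–15%, 30–70% of deaths untreated)
- Low end: 0.10 × 0.30 = 0.030, or 3.0 points; 0.030 × 450 = 13.5 patients.
- High end: 0.15 × 0.70 = 0.105, or 10.5 points; 0.105 × 450 = 47.25 patients.

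**Any oxygen** (assumed m up to 15%, 0–10% of deaths untreated)
- 0 to 0.15 × 0.10 = 0.015, so 0 to 1.5 points.

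**Wider range** (assumed m = 5–20%, q = 30–80%)
- Low end: 0.05 × 0.20 = 1.0 point, or 4.5 patients. High end: 0.20 × 0.70 = 14.0 points, or 63 patients.

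**Numerical check.** In 300 simulated cohorts of 450 (68 treated, 23 dead without treatment, 359 neither, all followed to day 28), the SAP rule gives 91/450 = 20.2%. The share treated is 68/450 = 15.1%, and an Aalen-Johansen estimate with death as a competing event also returns 15.1%.

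**By-type oxygen rows.** The same formula applies, with q now the share of deaths with that oxygen type recorded. The documents give no basis for a value, so no size is put on it.

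**What the rule cannot distort.** A treatment already in use at baseline, such as ventilation in score 2, is an event before any death can be.

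**The case against.** **The rule is prespecified, openly stated and a legitimate composite.** This stands in part. Counting death as an event is a recognised choice and it is written in the methods cell. But the same cell says that the quantity is the proportion admitted or ventilated, and the results table carries no hint of death. The defect is the mismatch between rule and label, not the composite itself.

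**The size rests on assumptions.** This stands for the figures. The direction and the formula need none.

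**The log-rank test.** A reader might infer that the planned test will often report a difference in ICU use that is only a difference in deaths. Simulating score 3–4 (n = 320) against score 5 (n = 110), both with 20% recorded ICU use, and with 5%, 8% or 10.5% against 1% dying untreated, does give p < 0.05 in about 12%, 23% and 41% of samples with full follow-up. That is a two-group test timed from admission. The SAP plans three groups timed from first symptom. When the remaining 450 − 320 − 110 = 20 patients are added as score 2 and assumed to be in ICU at baseline, the three-group test rejects in 100% of samples with or without the death rule. For ventilation the separation is definitional. The SAP specifies no pairwise contrast and, in section 2, no formal hypothesis. No false-positive rate can therefore be attached to the planned test.

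**Censoring at discharge.** A reader might also infer further inflation, because SAP 4.2 heads a data-collection column "last observation if discharged or died prior to these time points". But 8.2 names only the last observation date for these endpoints, and elsewhere the SAP lists discharge and last observation as separate items. The documents do not settle which date is used. It is a separate issue, and no size is claimed for it here.

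**Score 2 oxygen rows.** An excess of 10–40 points in that column is possible if 20–40% die and 50–100% of those deaths lack a record of that oxygen type. Nothing in the documents supports that lack of records, and a clock starting at first symptom could pick up oxygen given earlier.

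**Conclusion.** The point holds as a mismatch between the analysis rule and what is reported. Followed exactly, the SAP will present deaths without treatment as treatment use for endpoints 4.1, 5 and 7.1. On complete follow-up to day 28 and the main assumed rates, the overstatement is 3.0–10.5 points for ICU or ventilation and probably no more than 1.5 points for any oxygen; for the by-type oxygen rows it is unknown.

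The severity contrasts mix deaths with use of care, but the overall p-value for ICU and ventilation is likely to be driven by score 2 being ventilated at baseline. The documents do not support calling the composite invalid or the planned test inflated. The endpoints are secondary and descriptive, and the primary mortality analysis does not use this rule. It should be corrected before the tables are produced.

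**What to change.** - For endpoints 4.1, 5 and 7.1, count an event only when the treatment was recorded.
- Report n/N with a Clopper-Pearson interval and compare the groups by chi-square, as SAP section 9 already does for endpoint 10. If timing is wanted, report cumulative incidence with death as a competing event instead, keeping patients discharged alive without the treatment in the risk set to day 28.
- State that the count rows in Table 2 hold recorded events only.
- If the composite is wanted, keep it as an additional row named '[treatment] or death'.

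The cost is SAP wording, table labels and at most a few extra rows. No new data are needed: n/N requires a yes/no per treatment, and 8.2 already relies on start and end dates for oxygen, ICU and ventilation. The downside is slightly longer reporting, and n/N does not use timing.
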